SEARCH 4 Protocol Version 3: March 2, 2017 SUMMARY OF CHANGES

Page 7-8 (Table 3), Updated description of cohort survey-only recruitment targets Page 8 (Table 3), Echocardiogram recruitment update (CA site not participating) Page 9, 14, Addition of miRNA collection for storage (cohort participants)

SEARCH 4 Protocol Version 2: February 11, 2016 SUMMARY OF CHANGES

- Page 1, Funding mechanisms identified for Registry Study
- Page 2, Specific Aims for Registry Study
- Page 2, Funding mechanisms identified for Cohort Study
- Page 3, Cohort sampling (subset of SEARCH 3)
- Page 3, Summary of new measures in Cohort Study
- Page 3, Specific Aims for Cohort Study
- Page 5, New unit: Cardiovascular Reading Center
- Page 5, Incident year cohorts to be completed and/or initiated in Registry Study
- Page 6, Estimated number of registered cases
- Page 6, Sampling plan for Registry Study in-person visit
- Page 7, Sampling plan for Cohort Study visit (changes in Version 1 and Version 2)
- Page 7, Sampling plan for echocardiogram visit and survey-only cohort
- Page 8, Period of mortality follow-up
- Page 8, Informed consent for surveys obtained online (web-based)
- Page 9, Transfer of data and samples to NIDDK Repository
- Page 11, Update to laboratory measures obtained in IPV
- Page 12-15, New measures to be obtained in Cohort Study (survey instruments, echocardiography, neurocognitive)
- Page 16-19, Development & Validation Projects
- Page 19-21, Statistical considerations for Registry Study
- Page 22-24, Statistical considerations for Cohort Study
- Page 25, Centralized data management system
- Page 26, Alert values related to albuminuria, echocardiogram
- Page 28-30, Revisions to Appendix A

SEARCH for Diabetes in Youth

Phase 4 Protocol

September 30, 2015 - September 29, 2020

Version 1: October 30, 2015

Version 2: February 11, 2016

Table of Contents

1.	BA	CKO	GROUND	. 1
2.	OB	JEC	CTIVES	. 1
	2.1	RE	GISTRY STUDY OBJECTIVES	. 1
	2.2	CO	HORT STUDY OBJECTIVES	2
3.	ST	UDY	POPULATION	. 4
	3.1.	STU	UDY SITES	. 4
	3.2.	OT	HER SITES	. 4
	3.3.	STU	UDY POPULATION AND ELIGIBILITY	. 5
	3.3.	1.	The SEARCH Registry Study	. 5
	3.3.	.2.	The SEARCH Cohort Study	. 7
	3.4.	INF	FORMED CONSENT	. 8
	3.5.	RE	CRUITMENT & RETENTION	. 9
4.	ST	UDY	MEASUREMENTS	10
2	4.1.	ME	ASUREMENTS - REGISTRY STUDY	10
Z	4.2.	ME	ASUREMENTS - COHORT STUDY	12
5.	DE	VEI	LOPMENT AND VALIDATION PROJECTS	16
4	5.1.	PR	OJECT #1: CASE ASCERTAINMENT BY DIABETES TYPE	17

Diabetes is the third most prevalent severe chronic disease of childhood (1), and a leading cause of nephropathy, retinopathy, neuropathy, and cardiovascular disease (CVD) later in life. Although there is some evidence that rates of mortality, renal failure, and neuropathy have declined in young adults with youth-onset T1D diagnosed between the 1950s and 1980s (2), data from more contemporary cohorts are scarce. In addition, clinical care for childhood diabetes has evolved, now encompassing new insulin types and delivery systems, and new systems for monitoring glycemic excursions. Concurrently, the epidemiology of diabetes has evolved. The incidence rates of T1D have increased around the world (3, 4) and we have learned from the SEARCH for Diabetes in Youth Study that substantial proportions of adolescent minority youth now have T1D (5). Within the last two decades pediatric T2D has gone from infrequent to 15% of all diagnoses of diabetes in youth (6). Trends in the prevalence and incidence of T1 and T2D in young people are changing. Worldwide, from 1990 to 2008, the incidence of T1D increased by 2.8-4% per year (7), similar to that observed in SEARCH (8). Moreover, SEARCH demonstrated an increased prevalence of T1D between 2001 and 2009 (9). On the other hand, a recent report from Finland, with the world's highest incidence, suggested that the increase in incidence from 2005-2011 has stabilized (10). Regarding T2D, although few longitudinal studies have been conducted, there is evidence that the increase in T2D in youth stems from the increased frequency of obesity in pediatric populations (11). Interestingly, data from SEARCH suggest that prevalence of T2D may not be increasing equally across race/ethnic groups (9). Thus, there is much to be gained in studying the continued trends in incidence and prevalence of T1 and T2D.

2. Objectives

This is the fourth phase of the ongoing SEARCH for Diabetes in Youth Study. SEARCH phases 1-3 were conducted in 2000-2005, 2005-2010, and 2010-2015, respectively, and included both a registry component and a cohort component. Study methods (12) and highlights of SEARCH study findings (13) have been published and protocols are available online (www.searchfordiabetes.org). Unlike SEARCH phases 1-3, SEARCH 4 is supported by two separate grants from different funding agencies, one for the Registry Study (CDC) and one for the Cohort Study (NIH/NIDDK).

2.1 REGISTRY STUDY OBJECTIVES

In response to RFA-DP-15-002, and with funds awarded by the CDC with contribution from the NIH/NIDDK, SEARCH 4 will continue to ascertain newly diagnosed incident diabetes cases throughout the study period and one additional prevalent cohort (index year 2017) for youth age < 20 years across five geographically dispersed study centers that encompass the racial/ethnic diversity of the United States. Surveillance is framed as a tiered approach, starting with the most broad based and cost efficient approach at the highest tier (tier 1) and becoming the most focused in tier 3, optimizing use of electronic health data.

Aim 1: TIER 1 SURVEILLANCE - To ascertain prevalent diabetes cases in calendar year 2017 among youth age < 20 years at diagnosis. Research Question 1.1 What is the prevalence of diabetes in 2017, overall and by age, sex, race/ethnicity, and diabetes type? Research Question 1.2 What are the temporal trends in T1D and T2D prevalence over the three prevalent cohorts (2001, 2009, and 2017) and how do trends differ by race/ethnicity, age, and sex?

Aim 2: TIER 2 SURVEILLANCE - To continue to ascertain newly diagnosed (incident 2013-2020) diabetes cases in youth age < 20 years. Research Question 2.1 What are the temporal trends in T1D and T2D incidence since 2002 in US youth and how do trends differ by race/ethnicity, age, and sex?

Aim 3: TIER 3 SURVEILLANCE - To further determine agreement between the etiological classification of diabetes type using biochemical markers and provider assessment, to describe selected clinical characteristics at diagnosis, and to establish an infrastructure that facilitates the development of more detailed ancillary studies by storing biological samples and preserving contact with potential study participants. Data is extracted from EHRs in all incident years and an in-person visit is planned for incident cohort year 2016, using a strategic sampling plan to minimize cost. Research Question 3.1 Is the proportion of youth with provider diagnosed T1D or T2D who have biochemical evidence of these respective diagnoses consistent over time? Evidence is based on diabetes etiologic types previously established and employed by SEARCH using diabetes autoantibodies (DAA) and the insulin sensitivity (IS) score. Research Question 3.2 Has the prevalence of DKA near the time of diagnosis decreased over time for youth with T1D or T2D?

Aim 4: OPERATIONAL EFFICIENCY - To optimize efficiency of SEARCH surveillance activities through targeted Development and Validation (D&V) Projects designed to utilize electronic health data to operationalize each of the three tiers of surveillance to the extent possible. Methods employ electronic algorithms and text mining/natural language processing with validation, incorporating data from administrative records, medical records including provider notes, pharmacy, and laboratory data. We will then evaluate these approaches with a goal of identifying a model for targeted expansion of the SEARCH Registry to non-SEARCH sites.

2.2 COHORT STUDY OBJECTIVES

In response to RFA DK-14-508, and with funds provided by Special Statuary Funds for T1 Diabetes Research, SEARCH 4 will continue to follow selected incident cohorts from the SEARCH registry. Incident cohorts of youth from 2002-2006, 2008 and 2012 were asked to participate in a baseline research visit where history, demographics, health-care related variables, clinical information and factors essential for the etiologic classification of diabetes type (diabetes related-autoantibodies and markers of insulin sensitivity) (14, 15) were collected near diagnosis. Participants were asked to return at 1, 2, and 5 years from baseline

for repeated measures in SEARCH phase 1 and 2. During SEARCH 3 (2010-2015), individuals who had participated in a baseline visit with at least five years duration were invited to participate in a cohort visit. At the close of SEARCH 3, 2780 individuals participated for a final response rate of 72% among eligible individuals. The current protocol (SEARCH 4 Cohort Study) will follow a subset of this cohort (as well as a subset of participants who completed a 2012 Registry In Person Visit) with another assessment to further assess risk factors, acute and chronic complications, as well as QOL-related outcomes and add measures of cardiac structure and function, neurocognitive outcomes, and social functioning and stress. We will also continue to assess mortality and causes of death.

Aim 1: Establish, compare and contrast the burden (prevalence, incidence, progression and clustering) of acute and chronic complications of diabetes, and explore the responsible risk factors and pathways among youth and young adults with T1D and T2D. We will measure key outcomes, including: retinopathy, nephropathy, cardiac autonomic (CAN) and peripheral neuropathy, arterial stiffness, cardiac damage, neurocognitive outcomes, as well as acute complications (hypoglycemia, diabetic ketoacidosis -DKA). We will explore a variety of risk factors and pathways, including: metabolic; inflammatory; vascular; behavioral; socio- economic; psycho-social and healthcare factors. We hypothesize that: 1.1: Youth with T2D have higher prevalence, incidence, faster rate of progression and different patterns of clustering of chronic complications, but lower burden of acute complications than youth with T1D, independent of age, sex, diabetes duration and race/ethnicity; 1.2: The risk factor patterns associated with these outcomes are different in T2D vs. T1D.

Aim 2: Explore, compare and contrast processes of care (including barriers to care and quality of care- QOC) and their influence on QOL among youth with T1D and T2D, as they transition from pediatric to adult care. Measures to assess barriers include: consistent health insurance, out of pocket costs, continuity of care, employment, completion of education, finances, stressors from independence (school, work, marriage, children), social support, depression and neurocognitive factors. QOC variables include: frequency of visits with diabetes provider and receipt of screening for retinopathy, nephrology, neuropathy, foot exams, blood pressure and A1c. We hypothesize that: 2.1: Compared to youth with T1D, youth with T2D will a) have more and different barriers to care; b) benefit less from emerging treatment technologies; c) have worsening QOC and QOL as they transition from pediatric to adult care.

Aim 3: Conduct surveillance of mortality including cause of death in the SEARCH cohort. We hypothesize that: **3.1:** The frequency and causes of mortality in patients with youth-onset diabetes are different than among non-diabetic, age, sex and race/ethnicity comparable persons; **3.2**: Youth and young adults with T2D have higher mortality and different causes of death than youth with T1D, independent of age, sex, diabetes duration and race/ethnicity.

Aim 4: Maintain, supplement and promote access to the SEARCH Cohort repository for biological specimens to conduct scientifically and logistically appropriate ancillary studies.

3. Study Population

3.1. STUDY SITES

The five clinical centers that participated in SEARCH 3 will continue their participation in SEARCH 4. These sites are based in Ohio, Colorado, Washington, South Carolina, and California. Four SEARCH centers (Ohio, Colorado, Washington, and South Carolina) are geographically based - that is, newly diagnosed diabetes cases are identified from a geographically defined population. One SEARCH center (California) is membership-based - that is, newly diagnosed diabetes cases are identified from the participating health plan. Each of the five centers participates in both the Registry and the Cohort Studies.

- 1. Ohio Cases ascertained from Cincinnati and the 8 surrounding counties; oversight, recruitment and clinic visits provided by Children's Hospital Medical Center.
- 2. Colorado Cases ascertained from the state of Colorado and members of the Navajo Indian tribe in AZ, UT, or NM residing on the Navajo Nation reservation; oversight, recruitment and clinic visits provided by University of Colorado, Denver.
- 3. Washington Cases ascertained from Seattle and Tacoma and the 5 surrounding counties; oversight, recruitment and clinic visits provided by Seattle Children's Research Institute.
- 4. Carolinas Cases ascertained from the state of South Carolina with oversight provided by the University of North Carolina at Chapel Hill. Sub-centers are located at three locations in SC (Charleston, Greenville, Columbia) to assist with recruitment and clinic visits.
- 5. California Cases ascertained from Kaiser Permanente Southern California Health Care Plan membership (other than San Diego) with oversight, recruitment and clinical visits provided by the same.

3.3. STUDY POPULATION AND ELIGIBILITY

3.3.1. The SEARCH Registry Study

Over the three phases of SEARCH, investigators have registered more than 25,000 cases of youth with diabetes, including completed incident cohorts from 2002-2012, prevalent cohorts in 2001 and 2009, and ongoing efforts for registration of incident 2013-2015 cohorts. During SEARCH Phase 4, incident 2013-2017 cohorts will be completed, and incident 2018-2020 will be initiated but not completed (Table 1).

Table 1. Surveillance activities during SEARCH Phase 4						
Phase 4 Period	Case ascertainment of	Incident year to be closed				
	youth diagnosed in:	(30 months after the end of				
		the incident year):				
Yr1: Oct 2015-Sept 2016	2013, 2014, 2015, 2016*	2013				
Yr2: Oct 2016-Sept 2017	2014, 2015, 2016*, 2017	2014				
Yr3: Oct 2017-Sept 2018	2015, 2016*, 2017, 2018+	2015				
Yr4: Oct 2018-Sept 2019	2016*, 2017, 2018+, 2019+	2016				
Yr5: Oct 2019-Sept 2020	2017, 2018+, 2019+, 2020+	2017				
 + Registration for incident years 2018, 2019, and 2020 will not be completed during SEARCH 4. We will begin registering these cases in anticipation of future funding to fully register these incident years. Note that incident years 2013- 2015 initially began registration during SEARCH 3. *In-person-visits (IPV) will be conducted on 2016 incident cases. Yr=Year. 						

Registry Aims 1 and 2. Centers in SEARCH Phase 4 will continue to conduct populationbased ascertainment of cases of diabetes in youth less than 20 years of age for incident years 2013 through 2020, using methods consistent with those employed in SEARCH Phases 1-3. Prevalent cases will be obtained in index year 2017. Briefly, cases are ascertained primarily though networks of pediatric endocrinologists, with pediatric diabetes databases, electronic health records from participating inpatient and outpatient settings, hospitals, and other health care organizations being queried to identify the remainder of the cases. Cases will be validated based on physician reports, medical records reviews or self-reports of a physician diagnosis of diabetes based on an established set of criteria. Further eligibility is defined by the following: 1) children/youth who, in addition to having an onset of physician-diagnosed diabetes in the index year, are also are < 20 years of age on December 31 of the index year; 2) are resident of the population defined for geographically-based centers at any time during the index year, or a member of the participating health plan for the membership-based center at diagnosis, and 3) are not active duty military personnel or institutionalized. Young women who develop gestational diabetes mellitus (GDM) but who are not diagnosed with diabetes when not pregnant are not eligible. Sites are provided a 30 month window after the close of the incident year to identify all potential cases. For example, for incident

year 2016, the window closes 6/30/2019 (Table 1). A total of 13,440 incident cases are expected to be registered during SEARCH Phase 4 (Table 2).

The prevalence study for 2017 will attempt to identify and validate all unique, eligible cases of diabetes in youth less than 20 years who are residing in or are members of the SEARCH geographic areas and health plans in 2017. Previous prevalence studies have been conducted in SEARCH in 2001 and 2009. A total of 1004 new prevalent cases not previously identified through the incidence study are expected to be registered (Table 2). Completeness of case ascertainment will continue to be monitored via capture-recapture analyses, as described in detail on the SEARCH website (16).

Table 2: Estimated Number of Registered Cases (Incident and Prevalent) and IPV, Overall and By Site,								
SEARCH 4								
Carolinas Ohio Colorado California Washington Total								
2013 Incident*	378	179	422	265	284	1511		
2014 Incident*	389	184	435	273	292	1557		
2015 Incident*	401	189	448	281	301	1603		
2016 Incident	413	195	461	290	310	1652		
2017 Incident	425	201	475	299	320	1701		
2018 Incident	438	207	489	307	329	1752		
2019 Incident	451	213	504	317	339	1805		
2020 Incident	465	220	519	326	349	1859		
Total Incident	3360	1588	3753	2358	2524	13,440		
2017 Prevalent**	57	112	86	508	241	1004		
Total Cases (I + P)	3417	1700	3839	2866	2765	14,444		
Total IPV***	207	81	220	171	153	832		

SEARCH 3 protocol. **Excludes incident 2017 cases, and all previously registered incident and prevalent cases included in the 2017 prevalent sample. *** IPV for 2016 incident cases.

The calculation of incidence and prevalence rates require information on the population at risk. Race-bridged post-censal estimates of the July 1 resident US population, released yearly by the National Center for Health Statistics, are used as the denominators for the geographic sites. Each file contains population estimates for each US county by single year of age, bridged-race, sex, and Hispanic origin. Active duty military are excluded. The membership site (California) uses July 1 health plan enrollment data by single year of age and sex as the denominator. Addresses for each of the members are geocoded and census block level data are used as a source of race/ethnicity (17). The Indian Health Service user population for eligible service units on the Navajo Nation, defined as persons age < 20 years with one or more visits in the past 3 years (including the index year) is used to estimate denominators for this Colorado sub-site.

Registry Aim 3. A sample of cases diagnosed in 2016 will be invited for an in-person visit (IPV). Cases eligible for the IPV will include all cases diagnosed during 2016 who are of minority race/ethnicity, those with a provider diagnosis of T2D, and 25% of non-Hispanic white youth with a provider diagnosis of T1D, randomly selected for invitation. This sampling plan will yield approximately 832 IPVs (Table 2).

3.3.2. The SEARCH Cohort Study

Cohort Study Follow-Up (Cohort Aims 1 and 2). A subset of SEARCH 3 Cohort (C_1) and SEARCH 3 Registry (R_1) participants will be invited for a SEARCH 4 in-person visit. The eligible group will include all SEARCH 3 (C₁ and R₁) participants with T2D, all minority youth with T1D, and a random sample of NHW youth with T1D. The Coordinating Center (CC) will provide a list of randomly selected NHW youth with T1D to be invited for participation such that all participants will be 10 years or older, have at least 3 years of time elapsed since their SEARCH 3 (C_1 or R_1) visit and have at least 5 years of duration of diabetes at the time of their planned SEARCH 4 IPV. NHW sampling is performed since based on the limited available budget it was determined that there was minimal gain in statistical power to invite all T1 NHW youth for a return visit and that all proposed analyses could be addressed with the random sample of NHW T1. Table 3 shows the total number of participants expected to complete a SEARCH 4 Cohort visit ($N \sim 1.846$) based on the proposed sampling. These estimates are based on an expected 75% response rate. In addition, the SEARCH 4 IPV will include a sample of 500 participants to be identified by the CC to have cardiac echocardiogram measurements taken. This sample will include 250 T1D and 250 T2D with representation from all five clinical sites and have racial/ethnic diversity.

The remainder of SEARCH 3 (C_1) participants will form the survey-only group with no IPV in SEARCH 4. The survey-only option will also be offered to individuals who are eligible but refuse participation in the IPV. The survey-only group will be asked to complete questionnaires by mail, phone or internet. Survey data will be combined from the IPV and survey-only participants (at least2,546) to address Aim 2.

Cohort Study, by Clinical Site							
Site	In-Person Visit	Echocardiogram	(Estimated) Survey Only				
Carolinas	434	140	150				
Ohio	298	130	150				
Colorado	504	130	225				
California	352	0	25				
Washington	258	50	150				
Total	1846	450	700				

Table 2. Number of Expected participants for each component of the SEARCH 4

Mortality follow up (Cohort Aim 3): All incident cases identified by the Registry study during calendar years 2002-2015 will be included in the mortality follow-up through 12/31/17 using the National Death Index (NDI) (18). This is the second mortality assessment, with the initial one done for incident cases identified during 2002-2008 and followed through 12/31/10. Mortality status will be obtained by matching with the NDI as soon as the NDI has complete data for 2017, usually ~18 months from the close of the time period. Conservatively, we estimate that there will be 89 additional deaths for a total of 130, using mortality rates from the prior period. This will allow us to examine cause-specific deaths in selected subgroups.

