Neuropathy	1344/283	5%	10%	81%				
Nephropathy	1172/268	20%	29%	85%				
Prevalence Comparisons (Cardiac echocardiography)								
LV hypertrophy	250/250	5%	13%	86%				

Longitudinal Models: We will use a longitudinal mixed effects analysis of covariance approach to make comparisons among groups which includes duration of diabetes as a time-varying covariate and participant as a random effect. This approach models the varying durations of disease prior to the initial visit, and the varying durations of time allowed by the data collection windows between visits. These mixed effects models are flexible to allow for non-linear relationships to be modeled over time, and permit random rates of progression.

To estimate the sample size needed to detect a significant difference with sufficient power, calculations were based on comparing measurements after adjusting for C_0 or C_1 data. If the correlation between measurements is moderate (0.50) then we have 80% power to detect a difference of 0.139 standard deviations (SD) for each outcome of interest. For example, based on data collected on a subset of SEARCH T1D participants, the standard deviation for PWV carotid-femoral was estimated to be 0.7 m/s, thus we would have 80% power to detect a difference of 0.10 m/s in progression of PWV between youth with T2D vs T1D.

Clustering of Outcomes: In addition to examining each endpoint separately, we have the opportunity to look simultaneously at several outcomes in the same analysis. We

will create variables that describe the co-occurrence (clustering) of outcomes for each participant and examine whether there are differences in the patterns of these clusters between T1D and T2D youth. Approaches will utilize ordinal logistic regression methods or longitudinal mixed models depending on whether the clustering outcome is a count or categorical. More sophisticated statistical methods may also be used such as principal components analyses to determine which risk factors may form different components.

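### The echocardiogram sample is 500 from five sites in the text but 450 from four in the site table, and Table 6 still bases its 86% power for LV hypertrophy on 250 per type

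*Protocol*

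**What the plan says.** Three places in the current protocol describe the echocardiogram sample.

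- **Section 3.3.2, text.** The Coordinating Center is to identify the sample: "the SEARCH 4 IPV will include a sample of 500 participants to be identified by the CC to have cardiac echocardiogram measurements taken". The next sentence fixes its make-up: "This sample will include 250 T1D and 250 T2D with representation from all five clinical sites".
- **Section 3.3.2, table by clinical site** (captioned "Number of Expected participants for each component of the SEARCH 4"). The columns are in-person visit, echocardiogram and survey only. The California row reads "California 352 0 25" and the bottom row reads "Total 1846 450 700".
- **Section 6.2.1, Table 6.** Under "Prevalence Comparisons (Cardiac echocardiography" the entry is "LV hypertrophy 250/250 5% 13% 86", where the last figure is the power in percent. The text above the table names Fisher's exact test with two-sided alpha 0.05.

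The summary of changes for protocol Version 3 has an entry that begins "Echocardiogram recruitment update (CA site not participating".

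**The concern.** The text and the table sit in one section and give different sample sizes (500 and 450) and different numbers of contributing sites (five and four). Table 6 follows the text, so its power is calculated for 50 more participants than the recruitment table provides.

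Table 6 presents its rows as primary outcomes, so its figures will be read as the design basis for the T1D versus T2D comparison of LV hypertrophy. Two things are at stake:

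- whether the stated power applies to the sample that will be recruited;
- whether the protocol correctly describes which sites the echocardiographic results cover. California accounts for 352 of 1,846 expected in-person visits (19%) and is the only membership-based center (section 3.1).

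There is also a practical gap. The Coordinating Center selects the sample, but the only stated allocation, 250 of each type, does not fit within 450.

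**Working it through.** **Inputs**

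- Text, section 3.3.2: 500 in total, 250 T1D and 250 T2D, five sites.
- Site table, section 3.3.2: Carolinas 140, Ohio 130, Colorado 130, California 0, Washington 50.
- Table 6: LV hypertrophy 5% in T1D and 13% in T2D, 250/250, power 86%.
- Test: Fisher's exact, alpha 0.05, two-sided.

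**Step 1: the table total.** 140 + 130 + 130 + 0 + 50 = 450. The column adds up, so the 450 is not a misprinted total. The shortfall is 500 − 450 = 50, and 50/500 = 10%.

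**Step 2: reproduce the stated power.** Let X be binomial(n1, 0.05) for T1D and Y binomial(n2, 0.13) for T2D. Power is the sum, over all pairs (x, y) whose two-sided Fisher p-value is at most 0.05, of P(X = x) × P(Y = y). The p-value for a pair is the sum of the hypergeometric probabilities, given x + y, that do not exceed that of the observed table. For n1 = n2 = 250 this gives 86.3%, in agreement with the stated 86%.

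**Step 3: repeat with 450.** The protocol gives no T1D/T2D split of the 450, so each split below is an assumption. The even split carries over the 1:1 ratio in the text.

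| T1D / T2D | Total | Fisher power, 5% vs 13% |
|---|---|---|
| 250 / 250 | 500 | 86.3% |
| 225 / 225 | 450 | 82.0% |
| 250 / 200 | 450 | 83.8% |
| 200 / 250 | 450 | 83.0% |
| 270 / 180 | 450 | 83.0% |
| 300 / 150 | 450 | 80.4% |

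None of the splits of 450 reaches 86%. At the even split the loss is 86.3 − 82.0 = 4.3 points, and the type II error rises from 13.7% to 18.0%.

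**Step 4: sensitivity to the method.** Normal approximations shift the level but show a similar loss. Without continuity correction, power is 88.0% at 250/250 and 84.5% at 225/225. With it, power is 84.6% and 80.2%. The drop is therefore about 3.5 to 4.4 points whichever method is used.

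**The case against.** The strongest reply is that this is a sentence and a table row left unrevised when California dropped out of the echocardiogram component. The Version 3 summary of changes announces that, the site table carries it, and a careful reader can tell which figure is current. No analysis method changes, and power stays above 80% at any near-even split. Section 4.2 also names left ventricular mass, a continuous measure, as the primary echocardiographic outcome, and the LV hypertrophy row says nothing about power for that.

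Most of this stands, and it limits the severity. It does not remove the point. The conflict lies within the current text and does not depend on the summary of changes. The LV hypertrophy row still appears in a table of primary outcomes with a power that 450 participants do not give. Knowing the intended total also does not supply the missing T1D/T2D split.

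A reader might go further and infer that 250 T2D participants could not be found outside California. The documents do not support this. The 382 T2D participants in section 6.2.2 are a power input for Aim 2. With the 2,000 T1D participants assumed there, they make 2,382, which exceeds the 1,846 in-person visits. Section 3.3.2 says that Aim 2 combines in-person and survey-only participants, and no T2D count by site is given. A reader might also infer that omitting California biases the T1D versus T2D comparison. Nothing in the protocol shows that; only the description of coverage is wrong.

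**Conclusion.** The inconsistency is real and moderate. Section 3.3.2 contradicts itself on the size of the echocardiogram sample and the number of sites, and Table 6 states a power for a sample larger than the site table provides. The 86% is correctly calculated for 250/250. For 450 it is about 82% at an even split and 80.4% at 300/150.

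These figures rest on the protocol's own rates of 5% and 13%, on Fisher's exact test, and on assumed splits. It would be too strong to call the comparison underpowered. Among the splits tried, power falls below 80% only at an extreme such as 350/100 (71.0%), and nothing in the protocol points to such a split.

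**What to change.** Bring the section 3.3.2 text, the site table and the LV hypertrophy row of Table 6 into agreement. If 450 at four sites is the plan:

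- change the text to 450 participants and state the expected T1D/T2D split;
- replace the five-site wording with the four contributing sites, and say that California is excluded;
- restate the LV hypertrophy row with the new numbers per type and the recalculated power (about 82% at 225/225), keeping the rates at 5% and 13%. Changing the assumed rates to preserve the old power would fit the effect size to the answer.

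If 500 at five sites is still intended, the site table should change instead, and Table 6 can stay as it is.

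Under the first option the cost is a few words and one table row, with a stated power about 4 points lower. Procedures and recruitment do not change. Under the second, 50 further echocardiograms and California's participation would be needed.
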